8.4 Analyses

8.4.1 Demographics and Baseline Characteristics

Demographic and baseline characteristics will be summarized by randomized treatment arm using descriptive statistics

8.4.2 Efficacy Analyses

All hypothesis testing will be two-sided on a significance level of 0.05 except for OS. A group sequential testing procedure will be applied to OS to control the overall type I error for interim and final analyses. The α spending function is described in [Section 8.1](#). If superiority in OS is demonstrated, a hierarchical hypothesis testing approach for the key secondary endpoints will be used to preserve a study-wise type I error rate at 0.05. The key secondary endpoints will be tested in the following hierarchical order:

1. ORR
2. PFS

The formal statistical testing for ORR will take place only if OS is statistically significant and the statistical testing for PFS will take place only if both OS and ORR are statistically significant.

8.4.2.1 Methods of Primary Endpoint

The OS distributions will be compared in two randomized arms at the interim and final analyses via two-sided, log-rank tests, stratified by region, MSKCC risk group, and number of prior anti-angiogenic therapy regimens in the advanced or metastatic setting. The interim analysis for OS is planned after 398 deaths have been observed. This formal comparison of OS will allow for early stopping for efficacy and the stopping boundaries will be derived based on the O'Brien and Fleming alpha spending function in EAST v5.4. If the analysis is performed exactly at 398 events, the study could be stopped by the DMC for efficacy if the p-value is ≤ 0.0148 . The nominal significance level for the final look of OS after 569 events would then be 0.0455. The OS curve, median and OS rates at 12, 18, and 24 months for each randomized arm will be estimated using the Kaplan-Meier product-limit method. Two-sided, 95% confidence intervals for median OS will be computed by Brookmeyer and Crowley method.⁵³ Similarly, two-sided, 95% confidence intervals for OS rates at 12, 18, and 24 months will be computed by Greenwood method. The hazard ratio (HR) and corresponding two-sided 100(1- α)% (adjusted for the interim analysis) CI will be estimated in a Cox proportional hazards model using randomized arm as a single covariate, stratified by the above factors.

8.4.2.2 Methods for Secondary Endpoint

ORR will be compared using a Cochran-Mantel Haenszel (CMH) two-sided test stratified by the same factors used above. An associated odds ratio and 95% CI will be calculated. The ORR and its corresponding 95% exact CI will also be calculated by Clopper-Pearson method for each randomized arm.

The PFS distributions will be compared in two randomized arms via a two-sided, log-rank test stratified by the same factors as for OS. Sensitivity analyses will be performed using different PFS definitions to assess the robustness of the primary analysis. The PFS curve, median and PFS rate at 6 months for each randomized arm will be estimated using the Kaplan-Meier product-limit method. Two-sided, 95% confidence intervals for median PFS will be computed by Brookmeyer and Crowley method.⁵⁴ Similarly, two-sided, 95% confidence interval for PFS rate at 6 months will be computed by Greenwood method. The hazard ratio (HR) and corresponding two-sided 95% CI's will be estimated in a Cox proportional hazards model using randomized arm as a single covariate, stratified by the above factors.

The duration of objective response (CR + PR) and its median will be estimated for each randomized arm using the Kaplan-Meier product-limit method and limited to responders only. Two-sided, 95% confidence intervals for median duration of objective response will be computed by Brookmeyer and Crowley.⁵⁴

PD-L1 IHC data and tumor sample characteristics will be listed and summarized. The distribution of PD-L1 expression will be investigated graphically by summary plots and individual subject plots. Summary statistics of PD-L1 expression by treatment group and across treatment groups will be provided.

To assess the potential association between PD-L1 expression and OS, OS curves and medians with 95% CIs will be estimated using Kaplan-Meier methodology by treatment group for each PD-L1 expression quartile and for subjects with a missing or indeterminate PD-L1 IHC result.

Potential associations with ORR and PFS will also be examined. If there is an indication of a meaningful association, additional analyses may be performed to further evaluate PD-L1 expression as a predictive biomarker.

8.4.3 Safety Analyses

Summary tables will be presented on safety parameters for each treatment arm. Toxicity rates (worst CTCAE grade per subject) of adverse events and specific laboratory tests will be tabulated.

8.4.4 Pharmacokinetic Analyses

The concentration vs time data obtained in this study will be combined with data from other studies in the clinical development program to develop a population PK model. This model will be used to evaluate the effects of intrinsic and extrinsic covariates on the PK of nivolumab and to determine measures of individual exposure (such as steady-state peak, trough, and time-averaged concentration). Model determined exposures will be used for exposure-response analyses of selected efficacy and safety end points. Results of population PK and exposure-response analyses will be reported separately.

8.4.5 Biomarker Analyses

Pharmacodynamic Analyses

To assess pharmacodynamic effects in serum, blood RNA, or PBMC obtained from subjects on each treatment arm, summary statistics for biomarkers of immunoregulatory activity (eg, IFN γ -inducible proteins, miRNAs, antibodies to tumor antigens, gene expression, immune cells) and their corresponding changes (or percent changes) from baseline will be tabulated by planned study visit. In addition, the time course of biomarker outcomes will be investigated graphically. If there is indication of a meaningful pattern across time, further analysis may be completed to characterize the relationship. Possible associations between changes in biomarker measures of interest and exposure to study drug will be explored graphically.

Pharmacogenomic and Exploratory Analyses

Potential relationships between biomarker data and efficacy or safety endpoints will be investigated as part of an analysis plan aimed at identifying baseline biomarkers that may be used to prospectively identify patients likely (or not likely) to respond to nivolumab and to identify subjects who may be predisposed to having adverse reactions to treatment. These exploratory predictive biomarker analyses will be completed with biomarkers measured in blood and in tumor samples and will focus primarily, as outlined in the exploratory objectives, on SNPs in select genes associated with immunity or on the expression of selected proteins in tumor

specimens, such as PD-1, PD-L1, and PD-L2. Similar analyses will be completed with data regarding serum-soluble factors, blood RNA and/or immune cell types.

Associations between biomarkers and efficacy measures will be analyzed on all subjects treated with at least one dose of study medication and with corresponding efficacy and biomarker measurements. Efficacy measures will include response, PFS, and OS. Demographic and case-history factors will be examined to determine whether stratification or adjustments should be made within the subsequent statistical analyses, and if necessary, the appropriate stratification or adjustment will be made.

Biomarkers will be summarized graphically as they relate to efficacy and safety endpoints, as applicable. Summary statistics will be tabulated. SNP allele frequencies will be summarized. The relationships between binary measures (eg, response) and candidate biomarkers will be investigated using logistic regression. Associations will be summarized in terms of point and interval estimates of hazard ratios, odds ratios, or other statistics, as appropriate for the analyses completed. Models to predict clinical activity based on combinations of biomarkers may also be investigated.

Additional post hoc statistical analyses not specified in the protocol, such as alternative modeling approaches may be completed. All analyses described in this section are based on the availability of the data.

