3 INVESTIGATIONAL PLAN

3.1 Study Design and Duration

This is a Phase 3, randomized, open-label study of nivolumab (BMS-936558) vs everolimus in subjects with advanced or metastatic RCC with a clear-cell component who have received one or two prior anti-angiogenic therapy regimens in the advanced or metastatic setting and no more than three total prior systemic treatment regimens in the advanced or metastatic setting. Subjects must have evidence of progression on or after the last treatment regimen received and within 6 months prior to study enrollment. Approximately 822 subjects will be randomized 1:1 and stratified by region (US/Canada vs W. Europe vs Rest of World), Memorial Sloan-Kettering Cancer Center (MSKCC) risk group (favorable- vs intermediate- vs poor-risk; see [Appendix 1](#)), and number of prior anti-angiogenic therapy regimens in the advanced or metastatic setting (1 vs 2) to receive nivolumab (3 mg/kg IV every 2 weeks) on Arm A or everolimus (10 mg po daily) on Arm B. No dose increases or reductions will be allowed for nivolumab. Dose modifications for everolimus will be allowed as per the approved product label or as per standard practice in countries where everolimus is not approved for the treatment of advanced RCC. Subjects will be assessed for response (RECIST 1.1) by CT or MRI beginning 8 weeks from randomization and continuing every 8 weeks for the first year and then every 12 weeks until progression or treatment discontinuation, whichever occurs later. Subjects will be allowed to continue study therapy after initial investigator-assessed RECIST 1.1-defined progression if they are assessed by the investigator to be deriving clinical benefit and tolerating study drug. Such subjects should discontinue study therapy when further progression is documented (see [Section 4.3.6](#)). The primary endpoint of this study is OS. The final analysis of OS will occur after approximately 569 events (ie, deaths) have occurred. An interim analysis of OS will occur after at least 398 events (70% of total OS events needed for final analysis) have occurred. ORR and PFS (each based on investigator assessments using RECIST 1.1 definitions) are key secondary endpoints that will be subject to hierarchical testing, with testing for ORR followed by testing for PFS, if appropriate. Other secondary endpoints include duration of objective response, association of OS with PD-L1 expression, incidence of adverse events, serious adverse events, and laboratory abnormalities, and disease-related symptom progression rate.

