5.6 Biomarker Assessments

A variety of factors that may impact immunomodulation and efficacy will be investigated in peripheral blood and in tumor specimens taken from all randomized subjects prior to treatment and as outlined in [Table 5.1-1](#), [Table 5.1-5](#) and [Table 5.1-6](#). Data from these investigations will be evaluated for pharmacodynamic effects, for associations with efficacy endpoints, (Response, OS, PFS), and/or for associations with safety (adverse events). Comparative analyses between the two treatment arms will be used to identify biomarkers with predictive versus prognostic value. Complete instructions on the collection, processing, handling, and shipment of all samples described herein will be provided in a separate lab procedure manual.

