5.6.1.1 Tumor Specimens

A formalin-fixed, paraffin-embedded tumor tissue block or unstained slides of tumor sample (archival or recent) for biomarker evaluation must be available for all subjects at study entry, and received by the central lab prior to subject randomization. In the case of unstained slides, a minimum of 10 slides are necessary to conduct the planned biomarker analyses. If a recent

biopsy has been collected and submitted, submission of archival tissue, if available, is still highly encouraged. In cases where retrospective H&E staining by the central lab determines insufficient tumor tissue is present for biomarker analyses, additional archived tissue may be requested by the sponsor, if available. Complete instructions on the collection, processing, handling, and shipment of all samples, including archival and fresh tumor biopsies, will be provided in a separate procedure manual. Samples sent must be from excisional, incisional or core needle biopsy. Fine needle aspiration and bone metastases are not adequate for submission.

A reference laboratory will receive the samples for IHC-based analyses aimed at determining the abundance of expression of proteins involved in PD-1 signaling, such as PD-1, PD-L1, and PD-L2. Additional IHC analyses may be completed to determine the relative abundance of other protein markers associated with T and NK cells and macrophages or with RCC disease progression, such as Carbonic anhydrase IX (CAIX). The abundance of each protein monitored (or combinations of proteins) will be correlated with clinical endpoints.

FFPE tissue may also be evaluated by fluorescent in-situ hybridization (FISH), genetic mutation detection methods, and/or by qRT-PCR as part of additional exploratory analyses of putative biomarkers thought to be associated with response or resistance to therapeutics used in the treatment of RCC. Such analyses will be completed retrospectively and within the scope of informed consent.

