8.2 Populations for Analyses

- All enrolled subjects: All subjects who signed an informed consent form and were registered into the IVRS
- All randomized subjects: All subjects who were randomized to any treatment arm in the study. This is the primary dataset for analyses of efficacy and baseline characteristics
- All treated subjects: All subjects who received any dose of nivolumab or everolimus. This is the primary dataset for dosing and safety
- PK subjects: All subjects with available serum time-concentration data from randomized subjects dosed with nivolumab
- Immunogenicity subjects: All subjects with available data from randomized subjects dosed with nivolumab
- All randomized PD-L1 measurable subjects: All randomized subjects with a measurable PD-L1 expression result (ie excludes indeterminable and unknown)
- Biomarker subjects: All subjects with available biomarker data from randomized subjects

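### Section 8.4.5 limits exploratory biomarker–efficacy associations to dosed subjects, against the randomized biomarker set of Section 8.2 and the between-arm purpose of Section 5.6 (minor)

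*Protocol*

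**What the plan says.** Protocol Section 8.4.5 fixes the analysis set for biomarkers against response, PFS and OS: "Associations between biomarkers and efficacy measures will be analyzed on all subjects treated with at least one dose of study medication", with the matching measurements also available. It labels the work exploratory: "These exploratory predictive biomarker analyses will be completed with biomarkers measured in blood and in tumor samples". PD-1, PD-L1 and PD-L2 are named as examples of tumor proteins.

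Section 8.2 defines the populations differently:

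- On all randomized subjects: "This is the primary dataset for analyses of efficacy and baseline characteristics".
- On the biomarker set: "Biomarker subjects: All subjects with available biomarker data from randomized subjects".
- On the PD-L1 set: "All randomized subjects with a measurable PD-L1 expression result".
- The treated set is assigned to dosing and safety.

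Section 5.6 gives the purpose: "Comparative analyses between the two treatment arms will be used to identify biomarkers with predictive versus prognostic value". Section 5.6.1.1 says that tumor tissue "must be available for all subjects at study entry, and received by the central lab prior to subject randomization".

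**The concern.** A marker is predictive if the treatment effect differs between marker levels. That is a statement about the contrast between arms within each level, and randomization supports it only if subjects are kept as randomized. Section 3.1 describes the design: "This is a Phase 3, randomized, open-label study of nivolumab (BMS-936558) vs everolimus". The assigned arm is therefore known before the first dose, and a decision not to start can depend on the arm and on the subject's condition. Section 6.1.1 foresees subjects who are randomized and never treated, since it sets a separate collection period for their serious adverse events.

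At stake is the reading of exploratory results as predictive rather than prognostic. A second, smaller problem is that PD-L1 against OS, PFS and response appears both in Section 8.4.2.2, without a dosing condition, and in Section 8.4.5, with one. The reader cannot tell which set governs the overlap.

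**Working it through.** **Which set applies.** The plan states no figure for this analysis, so the first step is to set the sections side by side.

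| Section | Set or purpose | Dosing condition |
|---|---|---|
| 5.6 | Specimens from all randomized subjects; arms compared | None |
| 8.2, biomarker subjects | Randomized, with biomarker data | None |
| 8.2, PD-L1 measurable | Randomized, with a result | None |
| 8.2, treated subjects | For dosing and safety | At least one dose |
| 8.4.2.2, PD-L1 with OS, ORR and PFS | No restriction stated | None |
| 8.4.5, markers with response, PFS and OS | Treated, with data | At least one dose |

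Only 8.4.5 adds a dosing condition to an efficacy analysis, and it gives no reason.

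**Which markers are affected.** Tumor tissue must reach the central laboratory before randomization, so a tumor-marker result can exist for an undosed subject, and OS runs from randomization (Section 8.3.1). Blood for serum factors, miRNA, RNA, PBMC and SNPs is drawn after randomization and before dosing (Table 5.1-6). An undosed subject may have no blood sample under either definition.

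**How many subjects.** No never-treated rate is given. With 822 randomized (Section 8.1), assumed rates give:

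- 1%: 822 × 0.01 ≈ 8
- 3%: 822 × 0.03 ≈ 25
- 5%: 822 × 0.05 ≈ 41
- 10%: 822 × 0.10 ≈ 82

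**When the predictive contrast is biased.** Let s₁ and s₀ be the shifts in log HR caused by the exclusion in marker-positive and marker-negative subjects. The log ratio of HRs moves by s₁ − s₀.

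- If non-starting is unrelated to prognosis, or is the same in both arms, both shifts are close to zero.
- If it differs by arm and relates to prognosis but not to the marker, s₁ ≈ s₀ and the difference cancels.
- A net shift needs all three: a difference by arm, a link to prognosis and a link to the marker.

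**Size, by simulation.** The inputs are assumptions except the HR of 0.76, which is the design value in Section 8.1 and is applied in both marker groups, so the true ratio of HRs is 1.00. Undosed subjects have 0.5 to 3 times the hazard of the others, 80% of them are marker-positive, and the larger loss is in the everolimus arm.

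| Undosed, nivolumab vs everolimus | Ratio of HRs among dosed subjects |
|---|---|
| 1% vs 1%, or 5% vs 5% | about 1.00 |
| 1% vs 3% | 0.99 to 1.03 |
| 1% vs 5% | 0.96 to 1.05 |
| 1% vs 10% | 0.93 to 1.13 |

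The cancellation can be seen directly. At 1% vs 10% with three times the hazard, if undosed subjects split evenly by marker, the two HRs become 0.843 and 0.844, a ratio of 1.00. With 80% of them marker-positive, the ratio is 1.13. A separate rerun used exponential survival, a control median of 14.8 months, 20 months of accrual, 42 months in total and half the subjects marker-positive. It agreed with the ranges above to within 0.03.

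**The case against.** The strongest reply is that the exploratory objective in Section 1.3.3 seeks markers other than PD-L1 in subjects receiving nivolumab, so a treated set follows its wording. That is a fair reading of the objective, but it does not remove the between-arm purpose in Section 5.6. Section 8.4.5 is not limited to the nivolumab arm either.

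It can also be said that calling all randomized subjects the primary efficacy set does not bar an exploratory analysis on another set, and that Section 8.2 does not say which analyses must use its biomarker set. This stands in part. What remains is that 8.2 defines a set for this kind of data and 8.4.5 departs from it without explanation.

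Several limits stand in full. First dose is due within 3 working days of randomization (Section 3.1), so few undosed subjects are likely. These analyses carry no alpha and no decision rule. Section 8.4.5 allows covariate adjustment and further post hoc analyses. Tissue that was received may still prove insufficient (Section 5.6.1.1).

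A reader might go further and infer that the PD-L1 conclusion is compromised. The documents do not support that. The secondary objective has its own randomized set in 8.2, an analysis in 8.4.2.2 without a dosing condition, and an interaction test with randomized arm in the Synopsis.

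**Conclusion.** The inconsistency is real and rests on stated text. Section 8.4.5 conditions exploratory efficacy associations on a post-randomization event, contrary to the biomarker set in 8.2 and to the comparison that 5.6 depends on. It is a minor point: no primary, key secondary or secondary PD-L1 conclusion depends on it, and in practice it concerns mainly tumor-tissue markers.

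A reader might infer that the randomized comparison is broken, or that bias has been shown. Neither follows. What is lost is protection. Bias in the predictive contrast needs non-starting to differ by arm and to relate to both prognosis and marker, and the documents give no rate from which to judge this. A shift in the treatment HR itself should not be read as a shift in the predictive contrast. For example, losing 4% of the control arm, at twice the hazard of the rest, moves the Cox HR by about 2.4% (0.76 × 1.024 ≈ 0.78). If those subjects are unrelated to the marker, both marker levels move alike.

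The sizes quoted rest on assumed undosed rates, hazards and marker mix.

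**What to change.** In Section 8.4.5, for associations with response, PFS and OS, replace the condition of at least one dose by the biomarker subjects of Section 8.2: all randomized subjects with the relevant baseline biomarker result, analysed by randomized arm. Keep the treated set for safety associations and on-treatment pharmacodynamic summaries, or as a sensitivity analysis. Add a sentence noting that undosed subjects may lack blood-marker samples.

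The cost is a change of wording. The population is already defined and tumor tissue is already collected before randomization. For blood markers the change may add few or no subjects, and no extra sampling is proposed.

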8.4.6 Outcomes Research Analyses

FKSI-DRS questionnaire completion rate, defined as the proportion of questionnaires actually received out of the expected number (ie, the number of subjects still on treatment or in follow-up), will be calculated and summarized at each assessment point.

The disease-related symptom progression rate and its corresponding 95% exact CI will also be calculated by the Clopper-Pearson method for each randomized arm. The same analysis will be conducted, where death and radiographic progression will be also considered as disease-related symptom progression.

The EQ-5D will be used to assess each subject's overall health status. The following two measures from EQ-5D are used for this study: a population preference-based health state utility score (EQ-5D Index) and each subject's overall health state on a visual analog scale (EQ-VAS). Both the EQ-5D Index and EQ-VAS have been shown to be reliable and valid for assessing health-related PROs in cancer patients.

The health resource utilization data will be utilized to conduct economic analyses. ^{54,55,56}

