- Subjects on nivolumab are re-dosed every 2 weeks with allowances for delay up to a maximum of 6 weeks from last dose (see [Sections 4.3.1.1](#) and [4.3.3.1](#)). Subjects on everolimus will continue daily oral dosing with allowances for delay up to a maximum of 6 weeks from last dose (see [Sections 4.3.1.2](#) and [4.3.3.2](#)). Subjects on both arms adhere to the same 4-week cycle length, with nivolumab arm (Arm A) subjects receiving 2 doses within the cycle.
- Treated subjects will be evaluated for response according to the RECIST 1.1 guidelines beginning 8 weeks from randomization (± 1 week) and continuing every 8 weeks (± 1 week) for the first 12 months from randomization, and then every 12 weeks (± 1 week) until disease progression or end of therapy, whichever occurs later.
- ePRO instruments will be completed according to [Table 5.1-2](#) & [Table 5.1-3](#). For subjects in the nivolumab extension phase, PRO assessments will be done according to the schedule in [Table 5.1-7](#) and [Table 5.1-8](#).
- This phase ends when the subject is discontinued from study therapy. For a complete list of reasons for treatment discontinuation, see [Section 3.5](#).

Follow-Up Phase:

- Begins when the decision to discontinue a subject from study therapy is made (no further treatment with study therapy).
- Two X follow-up visits include PK/immunogenicity samples only for subjects who received nivolumab (Arm A). Subjects in the nivolumab extension phase will have XX follow-up visits and will not provide PK and immunogenicity samples.
- Subjects that discontinue treatment for reasons other than disease progression will continue to have tumor assessments beginning 8 weeks from randomization (± 1 week) and continuing every 8 weeks (± 1 week) for the first 12 months from randomization and every 12 weeks (± 1 week) thereafter until disease progression is documented.
- Subjects will be followed for drug-related toxicities until these toxicities resolve, return to baseline, or are deemed irreversible.
- Subjects will be followed every 3 months for survival, to include subsequent anti-cancer therapy.
- ePRO instruments will be completed according to [Table 5.1-4](#).

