Laboratory Tests	X		For X01 (and XX01) ONLY, repeat at X02 (and XX02) if study drug related toxicity persists. To include CBC w/ differential, LFTs, BUN, creatinine, fasting serum lipids profile (total cholesterol, triglycerides, LDL, and HDL), fasting glucose, and TSH
Pregnancy Test	X		Serum or urine
Survival Status			
Subject Status	X	X	Every 3 months (Y and YY Survival Follow-ups may be accomplished by visit or phone contact), to include subsequent anti-cancer therapy.
Efficacy Assessments			
Tumor Assessments	X	X	Only for subjects without progression on study therapy. Tumor assessments should be continued every 8 wks (\pm 1 wk) from randomization (or first dose of nivolumab for the nivolumab extension phase) for the first 12 months, then every 12 weeks (\pm 1 wk) until disease progression is documented
Study Samples Arm A Only			
PK Samples	X		See Table 5.1-5; Only for subjects ORIGINALLY randomized to Arm A, not required for nivolumab extension phase
Immunogenicity Blood Sample	X		See Table 5.1-5; Only for subjects ORIGINALLY randomized to Arm A, not required for nivolumab extension phase

Table 5.1-4: Follow-Up Assessments (CA209025) - ALL Subjects			
Other			
Patient-Reported Outcome Measurements	X	X	Collect FKSI-DRS and EQ-5D at both “X” and “XX” follow-up visits Collect EQ-5D information either in person or via telephone at “Y” and “YY” survival visits, q3 months for 1 year, then q6 months (sect. 5.3.1)
Health Resource Utilization	X		

^a X visits as follow, X1 = 30 days from last dose \pm 7 days, or may be on date of discontinuation \pm 7 days if the date of discontinuation is more than 37 days after last dose. X2 = 100-121 days from last dose (ie, 70-84 days from X1); XX01 and XX02 follow the same timeframe, but from last dose from the nivolumab extension phase

^b Y, Survival visits continue every 3 months after X visits; YY, Survival visits continue every 3 months after the XX visits (nivolumab extension phase).

Table 5.1-5: Pharmacokinetic and Immunogenicity Sampling Schedule for Subjects Originally Randomized to the Nivolumab Arm				
Study Day^a	Time (Relative to Dosing) Hour	Time (Relative to Dosing) Hour: Min	Pharmacokinetic Blood Sample Schedule	Immunogenicity Blood Sample Schedule
Day -3 to +1 (post randomization)	0 (Predose)	00:00		X
Cycle 1 Day 1	1.0 (EOI) ^b	01:00	X	
Cycle 1 Dose 2	0 (Predose)	00:00	X	X
Cycle 2 Day 1	0 (Predose)	00:00	X	
Cycle 3 Day 1	0 (Predose)	00:00		
Cycle 4 Day 1	0 (Predose)	00:00	X	X

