5.3.1 Follow-up and Survival Procedures

Subjects will be monitored for safety according to [Table 5.1-4](#). During the 100 days after the last dose of study treatment, subjects will have two follow-up visits for safety. Safety assessments will include: review of concomitant medications, physical examination measurements, vital signs, performance status, laboratory measurements (CBC, serum chemistry, liver function and thyroid function), and assessment of signs and symptoms including AEs and SAEs. Beyond 100 days from the last dose of study treatment, subjects will be followed for ongoing drug-related adverse events until resolved, return to baseline or deemed irreversible, or until lost to follow-up, or withdrawal of study consent, or start of a subsequent anti-cancer therapy.

Blood samples will be collected for pharmacokinetics and immunogenicity as noted in [Table 5.1-5](#) (only for subjects randomized to nivolumab at the first 2 follow-up visits up to 100 days from the end of treatment, except for subjects that withdraw consent). For subjects treated in the nivolumab extension phase, blood samples for pharmacokinetics and immunogenicity will NOT be collected in the extension phase.

Patient reported outcome (PRO) assessments (FKSI-DRS and EQ-5D) will be administered at the first two follow-up visits prior to any study related procedures. Beyond the 100 days after discontinuation, the EQ-5D will be administered once every 3 months for the first 12 months, then once every 6 months thereafter, as permitted by local law. Each site will be provided with a touch screen electronic PC tablet for the subject's responses of the PRO questionnaire. Subjects will either enter the data directly on to the electronic PC tablet at the time office visits (direct contact) or will respond to the script version of the PRO questionnaire via telephone contact. If the responses are given by telephone, site personnel will enter the responses onto the PC tablet. The data will then be transferred to the ePRO vendor.

The PRO data collection will be according to [Table 5.1-4](#) until death, withdrawal of study consent, or lost to follow-up.

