8.3.2.5 Disease-Related Symptom Progression Rate

Disease-related symptom progression rate is defined as the proportion of randomized subjects who have disease-related symptom progression as measured by the FKSI-DRS.

The nine items of the FKSI-DRS are summarized into a symptom scale ranging in score from zero (0) to thirty six (36), with zero being the worst possible score and thirty six being the best possible score.⁵¹ The minimum important change in the FKSI-DRS used to define symptom progression is approximately a change of two points and that definition has been used for this mRCC symptom scale in other mRCC trials.^{40,51,52}

Disease-related symptom progression is defined as a decrease of two points in the FKSI-DRS relative to the subject's baseline FKSI-DRS score without returning to above that point during the remainder of the study.

FKSI-DRS questionnaire is completed at baseline, on Day 1 of each cycle (starting with cycle 2), and then at the X and XX follow-up visits.

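### As worded, the FKSI-DRS completion rate counts subjects who owe no questionnaire as expected, so it understates completion, increasingly at later cycles

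*Protocol*

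**What the plan says.** Section 8.4.6 gives one definition of the FKSI-DRS completion rate: "the proportion of questionnaires actually received out of the expected number (ie, the number of subjects still on treatment or in follow-up"). The rate "will be calculated and summarized at each assessment point". No separate denominator is given for cycle visits and follow-up visits.

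The collection schedule is stated consistently elsewhere:

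- Section 8.3.2.5: "FKSI-DRS questionnaire is completed at baseline, on Day 1 of each cycle (starting with cycle 2), and then at the X and XX follow-up visits".
- Table 5.1-4, X and XX visits: "Collect FKSI-DRS and EQ-5D at both “X” and “XX” follow-up visits".
- Table 5.1-4, survival visits: "Collect EQ-5D information either in person or via telephone at “Y” and “YY” survival visits".
- Section 5.3.1: "Beyond the 100 days after discontinuation, the EQ-5D will be administered once every 3 months for the first 12 months". FKSI-DRS is not named for that period.

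Section 3.1 says of the Follow-Up Phase: "Begins when the decision to discontinue a subject from study therapy is made (no further treatment with study therapy"). It lists three-monthly survival contact within the same phase.

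**The concern.** The numerator can come only from subjects who were due a form at that visit. The denominator, as worded, also takes in everyone who has stopped treatment and is still being followed. At Day 1 of a late cycle, many of those subjects are in survival follow-up and will never be asked for FKSI-DRS again. Those still in the X-visit window owe no cycle form either.

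This matters because the completion rate is the only summary of FKSI-DRS missingness in section 8.4.6. The endpoint it supports, disease-related symptom progression, requires a two-point decline with no later recovery (section 8.3.2.5), so missing later forms bear directly on how subjects are classified. A rate that falls because subjects stop treatment while alive would look like poor compliance. A reader could then discount the symptom endpoint for the wrong reason.

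**Working it through.** The protocol states no completion figure, so there is nothing to reproduce. The check compares the denominator with the schedule and then illustrates the size.

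**Who is counted and who owes a form**

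| Subject's status at a given cycle's Day 1 | FKSI-DRS due at that visit? | Counted as expected under 8.4.6 as worded? |
|---|---|---|
| On treatment | Yes | Yes |
| Off treatment, X visits pending | No (due at X1/X2 instead) | Yes |
| Off treatment, survival follow-up | No (EQ-5D only) | Yes |
| Dead | No | No |

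The second and third rows are the error. For any visit:

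rate as worded = true completion × (number due a form) ÷ (number on treatment or in follow-up).

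The last ratio cannot exceed 1, so the rate can only be understated. The ratio falls over time as long as subjects leave treatment faster than they die. Neither statement depends on the figures below.

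**Inputs for the illustration**

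- Median OS of 14.8 months on everolimus and 19.5 months on nivolumab: section 8.1.
- Median time on everolimus of 4.9 months: an assumption. It is the median PFS on everolimus in the earlier placebo-controlled Phase 3 trial described in section 1.4.3. PFS is only a proxy, because section 4.3.6 allows treatment beyond progression.
- True completion of 90% among subjects due a form: an assumption.
- Exponential times and no loss to follow-up: assumptions.

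**Formula at a cycle visit, time t in months**

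rate as worded = 0.90 × S_T(t) ÷ S_OS(t), with S(t) = 0.5^(t/median).

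**Everolimus**

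- Month 6: 0.5^(6/4.9) = 0.428 and 0.5^(6/14.8) = 0.755, so 0.90 × 0.428 ÷ 0.755 = 51%.
- Month 12: 0.5^(12/4.9) = 0.183 and 0.5^(12/14.8) = 0.570, so 0.90 × 0.183 ÷ 0.570 = 29%.
- At actual four-week cycle visits: cycle 4 gives 0.90 × 0.677 ÷ 0.879 = 69%, cycle 7 gives 0.90 × 0.458 ÷ 0.772 = 53%, and cycle 13 gives 0.90 × 0.210 ÷ 0.596 = 32%.
- If the treatment median is varied from 3.5 to 6.5 months, cycle 7 ranges from 39% to 65%.

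**Does the distortion differ by arm?** For nivolumab, an assumed treatment median of 4.9 to 8 months gives:

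- Month 6: 0.90 × 0.428 ÷ 0.808 = 48%, up to 0.90 × 0.595 ÷ 0.808 = 66%, against 51% on everolimus.
- Month 12: 25% to 49%, against 29% on everolimus.

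Both ranges include the everolimus value. Under the exponential model the two arms are distorted equally when 1/T − 1/19.5 = 1/4.9 − 1/14.8, where T is the nivolumab treatment median. That gives T = 1 ÷ (0.2041 − 0.0676 + 0.0513) = 5.3 months. A shorter T puts nivolumab below everolimus, and a longer T puts it above.

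**With the denominator limited to subjects due a form**, the illustrative rate is the assumed 90% at every visit in both arms.

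**The case against.** The strongest reply is that the two halves of the parenthesis match the two kinds of post-baseline visit: on treatment for cycle visits, in follow-up for X visits. A subject off treatment has no further cycle Day 1, so no form would be expected from that subject. X1 and X2 are timed from each subject's own last dose and survival visits come after them, so at an X visit nobody has yet entered survival follow-up. Read this way, the denominator is right at both kinds of visit. Some usage supports it: section 8.3.2.4 speaks of the first and second visits in follow-up when it means the X visits, and section 5.3 separates the X phase from survival follow-up.

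This reading is plausible and would remove the error. But section 8.4.6 does not state it. It joins both groups in one definition for every assessment point, and section 3.1 uses the follow-up phase to cover survival contact as well. The wording leaves the correct denominator to the programmer's good sense.

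It can also be said that visit-level rules belong in the statistical analysis plan, which is not at hand. That would answer a gap, but here the protocol states a rule, and the rule conflicts with its own schedule.

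A reader might go further and infer that the formula creates a spurious difference between arms. The planned survival medians differ, so unequal distortion is possible. Its size and direction depend on time on treatment in each arm, which the protocol does not give. The 8-month upper value used above for nivolumab has no source in the document. That stronger claim is not supported.

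**Conclusion.** The point holds as a minor one. Applied as worded, the section 8.4.6 denominator includes living, off-treatment subjects who owe no FKSI-DRS form, so completion is understated, and increasingly so at later cycles. The direction follows from the text. The size does not: about 51% at month 6 and 29% at month 12 on everolimus, in place of 90%, rests on exponential times, a 4.9-month treatment median borrowed from PFS in another trial, 90% true completion and no loss to follow-up.

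A difference in distortion between arms should not be claimed. The illustrative ranges span no difference.

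The rate is descriptive. The OS test, the ORR and PFS hierarchy, and the symptom progression rate, whose denominator is randomized subjects, are unchanged.

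**What to change.** In section 8.4.6, replace the parenthesis that explains the expected number with: the number of randomised subjects for whom FKSI-DRS is due at that assessment point (on treatment at that cycle's Day 1, or alive and due for the X1/X2 or XX1/XX2 visit), excluding Y/YY survival follow-up. Keep all randomised subjects as the denominator at baseline.

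The cost is one sentence. It needs no new data and no change to the collection schedule, and it leaves every efficacy analysis as it is. If a statistical analysis plan already defines expected forms by visit, the protocol wording should be brought into line with it.
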